3.11.2 Follow-up in relation to the device used in the clinical investigation

When the access to the device is denied, the subject is no longer able to access it via the Steam platform as the software locks the player out. The subject can then uninstall the game from their device.

3.11.3 Return of unused, expired or malfunctioning devices

The device is a software with a digital key that makes installation possible. Subjects can anytime choose to uninstall unused, expired, or malfunctioning software instances.

3.12 Compliance with the recognised ethical principles

3.12.1 Independent ethics committee (IEC)

The study is performed according to the Declaration of Helsinki and in line with local ethical regulations. The study will not commence until a favourable opinion has been obtained from the appropriate institutional ethics committee (IEC). Any significant alterations affecting ethical issues a formal protocol amendment will be issued and submitted to relevant IEC/IRB (institutional review board) for approval. The amendment will not be implemented until IEC/IRB approval, except in cases where immediate implementation is necessary to eliminate or prevent imminent hazard to the subjects.

3.12.2 Guidelines and regulations

The trial will be conducted in compliance with the protocol, International Conference of Harmonisation (ICH), Good Clinical Practice (GCP), the applicable regulatory requirement(s) and the Declaration of Helsinki.

3.12.3 Subject confidentiality

The investigator(s) will respect and protect the confidentiality of the subject in all possible ways. Subject personal information is pseudonymised. Only the investigator and the persons authorised to verify the quality and integrity of the study will have access to subject records where the subject can be identified. See also Appendix 2 - Tutkimuksen tiedote ja tutkittavan suostumus, and Appendix 4 - Privacy notice and impact assessment.

3.13 Description of the Informed consent process

The subjects that have read the recruitment information (Appendix 1 - Recruitment notice) and confirmed that they fulfil the criteria for the study, are guided to read information regarding the study (Appendix 2 - Participant information and consent form) that has been written in accordance to the Finnish law medical research act (9.4.1999 / 488).

Research subjects are entitled to withdraw their consent at any point prior to the completion of the research. They are informed of this before the start of the research. Withdrawal of consent and resulting withdrawal from the research shall not involve any negative consequences for the research subject which they are informed of. For other details regarding informed consent, please see Appendix 2.

After reading information about the study, the subject is asked to read a user agreement (Appendix 3 - Confidentiality obligation and right of use).

After reviewing both Appendix 2 and Appendix 3, the subject signs the informed consent digitally. For information regarding the safe storage of digital materials, please consult Appendix 4 - Privacy notice and impact assessment.

3.14 Safety reporting

3.14.1 Safety reporting procedures and timelines

For AE and SAE definitions, see 3.3.

The subjects are given health information regarding the device in the game (see Appendix 6 - Investigator's brochure). Should the subject experience an anticipated or unanticipated AE or an SAE, or an assumed or observed device deficiency, they are able to report them through the channels below. The subjects can:

- Provide any free-form feedback in in-game questionnaires presented 28 times during the intervention, which are monitored by the CSCs.
- Report game-related issues digitally into a Jira-based system that is accessible through the in-game main menu which is monitored by the CSCs.
- Describe their concerns in both subject-initiated and pre-scheduled (weeks 0, 4, 8, 12, and 24) phone calls with the CSCs.
- Send email to CSCs by using an email address presented both in the game main menu and in the subject's informed consent form.

The CSCs actively monitor these channels on a daily basis from Monday to Friday between 9-17 o'clock. When the subject indicates an AE, SEA, or device deficiency, the event is recorded into a secure, traceable digital system.

Timelines. The summary report for AE is delivered to the coordinating investigator on a weekly basis for review. AE that merit investigations are reported immediately to the coordinating investigator. All SAE are reported immediately to the coordinating investigator both verbally as well as in written reports.

Records. Coordinating investigators keeps a full digital record of any AE, SAE, and device deficiency. The coordinating investigator is responsible for evaluating whether the AE or SAE has a causal connection with the device use. The causality is evaluated on a scale of **possible**, **probable**, and **definitive**. In addition, the AE is evaluated for its severity from **mild** effects that are easily tolerated, **moderate** where there is discomfort, and **severe** that has significant effects. All device deficiencies are evaluated for the possibility of AE and SAE.

Follow-up. The coordinating investigator will follow the AE, SAE, or device deficiency with examining its connection with the device use. When necessary, a patch process is undertaken as described in 3.14.2 The AE and device deficiency are reported to regulatory bodies, including FIMEA and HUS ethical board, according to regulatory schedules. SEA are reported without delay and within a maximum of 7 days to the relevant regulatory bodies as well as research sites.

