3.7 Statistical considerations

3.7.1 Data descriptors and frequency

Data for the analysis of the clinical study will be collected in the forms of:

1. **Sign-up process.** The online sign-up process is done once at the beginning of the study where the subject gains information regarding the study, signs an informed consent form, and background information is gathered.
2. **Clinical questionnaires.** The subjects fill questionnaires prior to the intervention (T0), and 4 (T1), 8 (T2), 12 (T3), and 24 (T4) weeks from the beginning of the research.
3. **In-game questionnaire.** An in-game questionnaire is presented to the subject after each game level, up to a total of 27 times, please see Appendix 7 - Tutkimuksessa kerättävät tiedot
4. **In-game behaviour.** Behavioural performance scores that are acquired from each completed game.
5. **Clinical interview.** The subjects are interviewed for the inclusion and exclusion criteria before the intervention begins.
6. **Experiential interview.** The subject may opt in to an interview conducted online.

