3.7.1.2 Clinical questionnaires

The subjects fill questionnaires prior to the intervention (T0), and 4 (T1), 8 (T2), 12 (T3), and 24 (T4) weeks from the beginning of the research. All questionnaires are answered online.

The subject must fill the questionnaires at T0 before they are randomised into one of the three research arms: the intervention doesn't begin before the subject has filled the questionnaires. At T1, T2, T3 and T4, the subjects have two weeks to fill the questionnaire from the beginning of the time point. If the subject doesn't fill the questionnaire within one week, they are followed up with a phone call.

ASSIST-LITE, PCL-5, and BEAQ are filled only once at T0. The state of care questionnaire is filled in T1, T2, T3, and T4. IEQ measures game experience and is filled only after the subject has played the game. Other clinical questionnaires are filled at T0, T1, T2, T3, and T4. (see also Table 5).

The questionnaires include:

- Immersive experiences questionnaire (IEQ)
- Questionnaire regarding their state of care
- Patient health questionnaire (PHQ-9)
- Quick inventory of depressive symptomatology (QIDS-SR16)
- General anxiety disorder questionnaire (GAD-7)
- Positive valence systems scale (PVSS)
- The ruminative response scale (RRS)
- Alcohol, smoking and substance involvement screening test lite (ASSIST-LITE)
- PTSD checklist for DSM-5 (PCL-5)
- Brief experiential avoidance questionnaire (BEAQ)
- Sheehan disability scale (SDS)
- Well-being index (WHO-5)
- 7 item game addiction scale (GAS)

For details when the subjects are asked to fill the questionnaire, see table 5. For the questionnaire descriptions see 3.6.5.1, and for questionnaire content, see Appendix 7 - Data collected in the study.

Table 5: Clinical questionnaires

	Content	Sign up and background questionnaires	T0 Before playing	T1: T0 + 4 weeks	T2: T0 + 8 weeks	T3: T0 + 12 weeks	T4: T0 + 24 weeks
1	Immersive experiences questionnaire (IEQ)			MEL-T01 MEL-S01	MEL-T01 MEL-S01	MEL-T01 MEL-S01	TAU
2	Treatment status -questionnaire			x	x	x	x
3	Patient health questionnaire (PHQ-9)		x	x	x	x	x
4	Quick inventory of depressive symptomatology (self-report) (QIDS-SR16)		x	x	x	x	x
5	General anxiety disorder questionnaire (GAD-7)		x	x	x	x	x
6	Positive Valence Systems Scale (PVSS)		x	x	x	x	x
7	Short-version ruminative response scale (RRS)		x	x	x	x	x
8	Alcohol, Smoking and Substance Involvement Screening Test (ASSIST-LITE)		x				
9	PTSD Checklist for DSM-5 (PCL-5)		x				

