3.7.1.3 In-game questionnaire

The in-game questionnaire occurs after each level achieved by the player. It asks two questions on a seven point scale: 1) does the subject enjoy the game; 2) how difficult did the subject find the game? In addition, the subject is able to mention other aspects considering their play experience. The questions (in Finnish) can be found in Appendix 7 - Data collected in the study.

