3.7.5.2 Criteria for “harmful”

We will consider the digital interventions (MEL-T01 or MEL-S01) to be harmful if TAU is superior to either intervention so that:

The reduction in PHQ-9 score from T0 to T3 is

greater for TAU than for MEL-T01

OR

greater for TAU than for MEL-S01.

If either of the superiority conditions are met in a one-tailed t-test (or in a one-tailed Wilcoxon test if the conditions defined in [3.7.3](#) for using a parametric test are not met) with a Bonferroni-corrected ($N_{\text{tests}} = 2$) alpha-level of 0.0125, we consider the digital intervention as harmful to the subjects and terminate the investigation immediately.

Here, it is important to note that, at the discretion of the investigators, it is also possible to halt or terminate the investigation on the basis of harmfulness also at times other than that of the Interim analysis. As described in [3.15.2.2](#), evidence for such harmfulness could be excessive AEs in many subjects or an SAE that is related to the investigational device and may potentially be experienced by other than the subject first reporting it.

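### In the supplied text no scheduled form asks about the 13 anticipated AEs, and two of the four reporting routes are closed to TAU before T3, so device-versus-TAU AE rates would rest on unequal ascertainment

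*Combined protocol and SAP*

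**What the plan says.** Section 3.14.1 sets out four ways in which a subject may report an AE, a serious AE or a device deficiency to the clinical subject coordinators (CSCs):

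1. the level-end questionnaire in the game: "Provide any free-form feedback in in-game questionnaires presented 28 times during the intervention, which are monitored by the CSCs";
2. an issue system in the game: "Report game-related issues digitally into a Jira-based system that is accessible through the in-game main menu";
3. phone calls, either started by the subject or "pre-scheduled (weeks 0, 4, 8, 12, and 24) phone calls with the CSCs";
4. email, to an address shown in the game menu and in the consent form.

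Section 3.7.1.3 describes the level-end questionnaire: "It asks two questions on a seven point scale", namely "does the subject enjoy the game; 2) how difficult did the subject find the game", with room for other remarks. Section 3.7.1 says it is "presented to the subject after each game level, up to a total of 27 times", against 28 in 3.14.1.

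On calls, 3.7.1.2 says "If the subject doesn't fill the questionnaire within one week, they are followed up with a phone call", and 3.10.1 repeats this with a limit of 7 days. The access table in 3.11.1 gives TAU subjects no device until T3.

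Two safety-related outcomes are collected on schedule in all arms. CSCs see the suicidality-related answers (3.6.3.5, 3.6.4.3), and the text of 3.7.1.2 places the game addiction scale (GAS) at T0 to T4.

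**The concern.** An AE rate can be compared between arms only if each arm has about the same chance of having an event recorded. Here the protocol names 13 events that it expects, some of which (headache, stress, dizziness, nausea) also occur in people with depression who play no game. The TAU arm is the only source of a background rate for these. If TAU subjects have fewer routes and fewer occasions to report, the device arms can look worse than TAU for that reason alone. If all arms under-report, a short AE list in the clinical investigation report cannot be told apart from poor capture.

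**Working it through.** **1. Scheduled forms against the list of anticipated AEs.** Sections 3.6.5.1 and 3.7.1.2 and Table 5 cover depression, anxiety, reward, rumination, substance use, PTSD, experiential avoidance, disability, well-being, game addiction, gambling, immersion and state of care. None is described as asking about the 13 events of 3.3.1.2. State of care asks about changes in treatment, not about AEs. Section 3.3.1.3 encourages subjects to report, and 3.14.1 says what they can do. Both leave the initiative with the subject.

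**2. Routes by group, T0 to T3.**

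| Route in 3.14.1 | Device arms, playing | Device arms, stopped playing | TAU |
|---|---|---|---|
| Level-end free text | yes, up to 27 or 28 occasions | no further occasions | no |
| In-game issue system | yes | yes while the menu can be opened; no after consent is withdrawn | no |
| Phone | yes | yes | yes |
| Email | yes | yes | yes |

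So 2 of 4 routes are closed to TAU in the controlled period. The level-end form is tied to progress: a subject who stops after two levels has seen it about twice. Section 3.3.1.2 guides a subject with an AE to stop playing and to report by the in-game link or email, so anyone who follows that guidance no longer meets the level-end form.

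**3. Calls.** Section 3.14.1 gives five scheduled calls. The week 0 call matches the eligibility call in 3.6.3.3. For T1 to T4, 3.7.1.2 and 3.10.1 mention calls only when forms are a week overdue, and 3.10.2 says that other contact between subjects and researchers is avoided. A subject who always answers on time may therefore receive four post-baseline calls (three of them, at weeks 4, 8 and 12, in the controlled period) or none.

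**4. Illustration of size.** The plan states no AE rate to reproduce for this trial. The only source rates are from the pilot in 3.3.1.1, where 16.7% reported frustration (9/54 = 16.67%). That figure serves here only as a convenient event rate; it is not a TAU background rate. Capture probabilities are assumptions.

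- Reported rate = true rate × capture. With equal true rates, the reported ratio equals the capture ratio.
- Numbers per arm: 800/3 ≈ 266 recruited, or 133 analysable (3.7.4.1).
- Chance of a nominal two-sided p < 0.05 = Φ{[|p1 − p2| − 1.96√(2p̄(1 − p̄)/n)] / √[(p1(1 − p1) + p2(1 − p2))/n]}.
- Example, 80% against 40%, n = 266: p1 = 0.167 × 0.80 = 0.1336; p2 = 0.167 × 0.40 = 0.0668; p̄ = 0.1002. The numerator is 0.0668 − 0.0510 = 0.0158 and the denominator 0.0259, giving Φ(0.61) = 0.73.

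| Assumed capture, device / TAU | Reported rates | Ratio | Chance, n = 266 | Chance, n = 133 |
|---|---|---|---|---|
| equal | equal | 1.0 | about 5% | about 5% |
| 80% / 60% | 13.4% / 10.0% | 1.33 | 22% | 13% |
| 80% / 40% | 13.4% / 6.7% | 2.0 | 73% | 44% |
| 90% / 30% | 15.0% / 5.0% | 3.0 | 97% | 78% |

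**The case against.** Several points on the other side are right and limit the concern.

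- Questionnaire content is in Appendix 7 and the CSC call in Appendix 5. Neither was supplied, so a standard AE question there cannot be excluded. Suicidality and game addiction are covered on schedule. A reader might infer that nothing in the trial asks about safety; the text does not support that.
- A reader might infer that capture is mainly in-game and that those who stop lose their channels. Phone and email are open to everyone. A subject who merely stops playing can still reach the menu during the 12 weeks and for two weeks after (3.11.1). Access is lost on withdrawal of consent (3.15.3). Those who leave forms unfilled are called under either reading of the call schedule.
- The call sections need not contradict each other. A scheduled call and a reminder call can coexist, and neither section says that only late responders are called. This is unclear, not a proven conflict.
- A reader might infer from "evidence for such harmfulness could be excessive AEs in many subjects" that the halting criterion cannot be applied without a TAU rate. Section 3.15.2.2 rests halting on the device being judged the cause, and 3.14.1 has causality assessed for each event. That judgement does not need a TAU rate.
- Section 3.7 plans no between-arm AE test.

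What remains is the absence of an AE checklist in the supplied text, the two routes closed to TAU, and the unclear call schedule. The lack of a planned test does not remove the problem, since AE rates shown by arm would still be read against each other.

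**Conclusion.** The concern holds in a limited form. As the supplied text stands, AE capture relies on the subject reporting, apart from suicidality responses and GAS, and opportunity differs between the device arms and TAU before T3. Device-versus-TAU AE rates would be affected by unequal ascertainment, and all arms are open to under-reporting.

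It does not follow that no arms can be compared. MEL-T01 and MEL-S01 are blinded to each other and share every channel; their comparison is less affected, although exposure to the level-end form still depends on progress.

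The size cannot be derived from the documents. The ratios of 1.33 to 3.0 above simply return the assumed capture ratios and show only what unequal capture could do. A reader should not take a twofold or threefold excess as a finding. The conclusion also assumes that Appendices 5 and 7 contain no AE question put to all arms. The 27 against 28 count is an inconsistency to tidy and has no bearing on the conclusion.

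**What to change.** - Add one identical page to the T1–T4 online questionnaires in all three arms: the 13 anticipated AEs as yes/no items, one item on any hospital admission or other serious event, and free text. It should cover the time since the last form and send an automatic alert to the CSC.
- Base between-arm AE rates on this page and state the denominator. List reports from in-game text, the issue system, calls and email separately. Keep every channel for safety monitoring and for any halting decision.
- Reconcile 3.14.1 with 3.7.1.2 and 3.10.1 on whether all subjects or only late responders are called, and align the count of 27 or 28.
- If Appendix 5 or 7 already holds a standard AE question for all arms, cite it in 3.14.1.

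Cost: a minor amendment, about a minute per visit, and higher reported AE counts than spontaneous reporting gives. If the page is added mid-trial, capture will be uneven over time. That matters because the synopsis planned completion for 31 December 2023 and the current version is dated 26 February 2024. If collection is too advanced for a new form, report AEs by channel and arm and make no device-versus-TAU rate claim.

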3.14.2 Device deficiencies and patch process

It is possible that the software bugs cause the program to function in an unintended way such as preventing the subject from making progress in the game or causing the program to shut down. These effects may or may not cause AE, such as frustration, to the subject.

The subject can report their complaints of device deficiencies digitally at any point in the channels indicated in 3.14.1. Like AE and SAE, device deficiency is recorded digitally. Device deficiencies are also considered whether they have led to AE for the subject.

In the case of a critical issue in the game version that, for example, prevents the subjects from using the game as intended, we are able to deliver targeted “patch” versions that fix the critical issue. These patch versions are divided into two categories: server patches and game version patches.

Patching is a normal industry procedure for fixing critical issues. A server patch is a correction at the server side. It may or may not need a game version patch along with it. Server patches include but are not limited to correcting game difficulty or correcting error situations that may prevent subjects from using the software. The principal reason for a server patch is to adjust issues that can not be adjusted with a game version patch.

Game version patches focus on correcting issues on the game client installed on the subject’s PC. This includes but is not limited to fixing game breaking error situations where the subject is no longer able to use the software because of a software issue.

The patch process always targets a specific issue and does not change the overall behaviour of the software described in this protocol. If an issue has been deemed necessary to patch, we will track all the changes to the game code and game version as described in section 3.2.5. This includes but is not limited to file changes, date, author, version number and game versions. This process ensures that the changes made are targeted correctly to fix the desired issue and that there are no undesired changes. The patching process will never change the intended device functioning or lead to any changes to the functional and technical features of the device, which are reported in this protocol.

In the case that a subject notifies us about a critical issue in the game version via phone, email, customer support tool or any other means, we will follow the following procedure. First these issues will be documented in a complaints log by the clinical subject coordinator. These complaint logs are managed in a cloud document repository as described in section 3.2.5. Next the situation will be analysed by the game team to make sure that it is a valid issue, meaning the issue requires a change to the game itself. We will then proceed to creating a patch version either to the game or to the server. The patch version will go through rigorous and documented testing before being released to the subjects to validate the patch has fixed the issue and to ensure that the rest of the game remains unaffected.

3.15 Criteria and procedures for follow-up

3.15.1 Subjects following the end

The MEL-T01 and MEL-S01 have a 12 week follow-up period after the playing intervention between T3 and T4. TAU has a playing period between T3 and T4.

All subjects are emailed after they have filled the T4 questionnaire when the study period ends for all of the groups. In this email, the subjects are told about the randomisation as well as which group they belonged to as explained in Appendix 2 (Participant information and consent form). The subject is informed that the research results will be published later. The

subject is asked for feedback regarding the study, and their questions regarding the study are answered. The subject is thanked for their participation. The subject is asked for feedback regarding the study, and their questions regarding the study are answered via email or phone.

The subject is compensated for their participation based on Social and health ministry 82/2011 §2: 50€ if they have played the game for at least 24 hours and answered all questionnaires; or 120€ if they have played the game at least 48 hours and answered all questionnaires.

